Page **3** of **17** Version Date: Lidocaine is frequently used for analgesia with PNE placement. This is often performed with injectable lidocaine, however, other forms can be considered to improve patient comfort and clinical success – namely through topical lidocaine patches. Up to 5% (35 mg) of lidocaine patches are absorbed topically, producing analgesia within 30 minutes with a half-life of 6 to 8 hours⁷. Transdermally absorbed lidocaine appears to have a very low rate of systemic absorption resulting in local analgesia and not anesthesia, a characteristic not shared with lidocaine infiltration. The exact mechanism of this differential effect is unknown, however, it is hypothesized that the lidocaine patch produces analgesia without blocking all the sensory and motor inputs in large, myelinated A- β sensory fibers ⁷. The value of this relatively rapid onset medication with analgesic effects and without the associated discomfort of infiltration can be increased comfort for patients. The ability to potentially detect adverse sensation more sensitively in the office may also make this method of analgesia more effective.

Objectives

Primary outcome will be:

• VAS pain scores measured on a 10 point scale before and after PNE procedure

Secondary outcomes will be:

- Patient Overall Satisfaction after PNE placement
- Volume of injectable lidocaine used
- Rate of successful PNE
- Progression to permanent SNS implantation.
- Amplitude of perineal stimulation

Page **4** of **17** Version Date: Our null hypothesis is that there will be no significant difference in change in VAS score between patients in the lidocaine patch group and the patients in the control group.

We hypothesize that patients in the lidocaine patch group will experience significantly less pain at the time of PNE as measured by change in VAS pain score when compared with the control group.

Study Design/Methodology

Patients who have been scheduled for a PNE procedure will be will be consented for the study on the day of the procedure and screened for participation prior to the procedure by phone. Participants will be randomized with a stratified block randomization scheme (with a random block size of 4, 6, and 8 participants). Randomization sequence will be generated by statistician collaboratorr. All data will be recorded in the RedCap software and be maintained in that password-protected format until analysis. Data analysis will be performed by researchers associated with the IRB for this study. De-identified data will also be sent to statistician collaborator for analysis. The trial is powered to detect a change in VAS pain score of 1.5 points or more on a 10 point scale, a value that is taken to be the minimum clinically meaningful change for the VAS instrument.^{8,9} Data on identification key will be deleted at the conclusion of this study. Patient enrollment will conclude when 34 subjects, 17 of each group, have been enrolled in the study. Sample size was determined using G*Power so that we have 80% power to detect a difference between groups of the minimum clinically meaningful effect size of 1.5 points or greater using the two-sample test at α =0.05 and an assumed standard deviation for VAS score of 1.5 points.

Inclusion criteria:

- 1. Female patients undergoing sacral neuromodulation for the management of their OAB with SMN trial with PNE without fluoroscopy.
- 2. No contraindication to the use of lidocaine patch
- 3. Age >18 years old

Exclusion criteria

- 1. Patients who are not candidates for SNM therapy
- 2. Patients with contraindication to SNM including pregnancy
- 3. Allergy to lidocaine or adhesives
- 4. Chronic pain as an indication for the PNE procedure

Study design

[figure not shown]
The study design will be a double-blind randomized control trial comparing 4% lidocaine patch placed over the sacrum 30 minutes prior to the procedure to placebo patch. Intervention and control patches will be in envelopes labeled with study number and located within the procedure area. A patch from the envelope corresponding to the patient will be placed by a medical assistant or co-investigator who is not associated with the PNE placement procedure 30 minutes prior to the procedure start. Number of voids and incontinence episodes per day

Page **6** of **17** Version Date: prior to the PNE procedure will be recorded. A patch (intervention or control) will be removed by a medical assistant prior to provider entering the room in order to secure blinding. 1% lidocaine will be injected into the sacral procedure site for adequate pain relief. PNE procedure will then be performed. If inadequate analgesia is reported by the Patient during the procedure, additional injectable lidocaine will be administered, not to exceed 4.5 mg/kg of injectable lidocaine. The volume of injectable lidocaine used will be recorded. VAS pain scores prior to and immediately after procedure will be recorded. Patient Satisfaction Score, rate of successful PNE, rate of progression to SNS implantation, and amplitude of perineal stimulation of a Likert scale will be collected immediately after the procedure.

Patients will follow up in 1 week – as is standard of care with the PNE procedure. Adverse events such as pain or change in sensation will be recorded. Number of voids and incontinence episodes per day after the PNE procedure will be recorded. Overall satisfaction score will be recorded at that time.

In summary, overall questionnaires and data being collected include:

Figure 1: Patient flow and outcomes:

Study has been registered on Clinicaltrials.gov

Participant Recruitment Methods

Subjects will be recruited from the ULP Female Pelvic Medicine and Reconstructive Surgery (FPMRS) practice at the University of Louisville Health Care Outpatient Center (HCOC), Urogynecology Associates office at [name] and the Springs Medical Center. All Patients receiving care at University of Louisville Urogynecology who meet screening criteria will be called prior to their PNE procedure to assess for willingness to participate in this study. Women meeting study criteria will be approached by a member of the research team for consent prior to their PNE procedure. Women interested in the study will have the study explained to them, the consent reviewed, and questions addressed in a confidential manner in a private room. At the time of consent, participants will be informed that their participation in this research is voluntary and that they may discontinue participation without penalty at any time. Participants will not be reimbursed for their participation in this research study.

Informed Consent Process

Patients will be called prior to their procedure to assess if they are interested in participation in this study. If they are interested, they will present with sufficient time prior to their procedure

to review and sign their consent form and have their patch (lidocaine vs placebo) placed (in place for 30 minutes). Consent form is otherwise attached.

Research Procedures

Please see study design/methodology section for further details. In addition all members of the research team will be educated on the study protocol at a division meeting or meeting set up for training purposes. All members of the research team will be able to ask questions at this education session and after the education session to ensure they are comfortable with all aspects of the study protocol. Members of the research staff that will be using REDCap (Research Electronic Data Capture) will be trained on how to use this database.

Minimizing Risks

Potential risk of breach of confidentiality will be mitigated by the redcap software and use of password protected University of Louisville computers for data entry and analysis. No one other than study investigators will be able to access data and it will be deleted at the conclusion of the study. Patient will be assigned a study number during the consent process and it will be associated with a patient identifier in REDCAP. No other location will have this information.

As this study is minimal risk there will not be oversight of the data. As this drug is available over the counter and is not investigational, it will be placed in envelopes at the start of the study and dispensed by investigators and clinic staff. All expected adverse events are of mild severity.

For this study, the following standard adverse event (AE) definitions are used:

- Adverse event: Any unfavorable and unintended sign, symptom, or disease temporally
 associated with the use of a medical treatment or procedure, regardless of whether it is
 considered related to the medical treatment or procedure.
- Serious Adverse Event (SAE): Any AE related to the study drug that results in any of the following circumstances: death, life-threatening, event requiring inpatient hospitalization or prolongation of existing hospitalization, persistent or significant disability/incapacity

AEs are graded according to the following scale:

- Mild: An experience that is transient and requires no special treatment or intervention. The experience does not generally interfere with usual daily activities.
- Moderate: An experience that is alleviated with simple therapeutic treatments. The experience impacts usual daily activities.
- Severe: An experience that require therapeutic intervention. The experience interrupts
 usual daily activities. If hospitalization (or prolongation of hospitalization) is required for
 treatment of something related to the study drug, it becomes a SAE.

The study uses the follow AE attribution scale:

- Not related: The AE is clearly not related to the study procedure (i.e., another cause of the event is most plausible and/or a clinically plausible temporal sequence is inconsistent with the onset of the event).
- Possibly related: An event that follows a reasonable temporal sequence from the initiation of study procedures, but that could readily have been produced by a number of other factors.
- Related: The AE is clearly related to the study procedures.

Expectedness of Adverse Events:

- Uncommon: discomfort over the area the lidocaine patch was placed and discomfort with the PNE procedure itself
- Rare: Allergy to adhesive bandage or lidocaine, lidocaine toxicity

Plan for Analysis of Results

Summary statistics for demographics, procedures variables, and outcome measures will be summarized for each treatment group (lidocaine patch and control patch) using means, standard deviations, counts and proportions, as appropriate. Differences in these variables will be assessed using the two-sample t-test for continuous variables and the Fisher exact test for categorical variables. A two-sample t-test will be used to assess differences in the primary outcome of change in VAS score after procedure between groups. Differences in secondary outcomes will be considered using the two-sample t-test for continuous variables and the Fisher exact test for categorical variables. Transformations and/or non-parametric methods will be used if continuous data are found to substantially violate the assumption of approximate normality. Multivariate linear/logistic regression models may be used to assess the impact of other variables onto primary or secondary outcomes. Throughout, a significance level of α =0.05 will be used, and all tests will be two-sided. Data analysis will be performed by a biostatistician collaborator using the R statistical software.

Research Materials, Records, and Privacy

Data that is to be collected with this study and entered into an encrypted database:

Demographic data

- Name
- Date of birth
- Age
- Weight
- BMI
- Race/ethnicity
- Smoking status
- Indication for PNE
- Contact information
- Randomization assignment

Page **13** of **17** Version Date:

- Study ID number
- Number of voids and incontinence episodes per day prior to the PNE procedure and 1

week after the PNE procedure

Procedural variables:

- Total amount of lidocaine used
- Side of PNE lead stimulated
- Amplitude of stimulation at completion of procedure
- VAS pain score prior to and after the PNE procedure.
- Satisfaction scale immediately post procedure and 1 week after the procedure.

1-week follow up variables:

- Adverse events of PNEs such as uncomfortable change in perineal sensation present at the 1 week post-procedure visit
- Patient satisfaction score immediately after the PNE procedure and at the 1 week postprocedure visit
- Number of days with successful stimulation
- Amplitude of stimulation at time of removal
- Bladder/ fecal diary with symptoms during the PNE trial period

3-month follow up

- Number of patients with a "successful" PNE who underwent an implantation
- Number of patients with a "successful" PNE who planned implantation but had not yet scheduled

Page **14** of **17** Version Date:

- Number of patients with a "unsuccessful" PNE who underwent staged procedure
- Number of patients with a "unsuccessful" PNE and what other treatment options they pursued in the next 3 months

Successful PNE is defined as PNE procedure which resulted in successful wire placement.

Unsuccessful PNE is defined as PNE procedure which did not result in successful wire placement.

Implantation defined as stage 2 procedure after interval PNE results showed >/=50% symptom reduction.

Staged procedure is a stage 1 procedure in the operating room as opposed to being performed as an outpatient PNE

This information will be sourced from the subjects themselves and questionnaire templates for satisfaction score and VAS pain score will be attached to this document as appendices. This information is necessary to display if the intervention results in an increased comfort with the PNE procedure or increased satisfaction with the procedure. Number of voids and incontinence episodes before and after the PNE procedure is recorded to examine if a change in procedural effectiveness occurs with this intervention.

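### Randomisation is stratified but the primary t-test ignores the strata; if the strata predict change in VAS, the test is conservative and gives up power at n = 34

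*Combined protocol and SAP*

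**What the plan says.** Study Design/Methodology sets the allocation: "Participants will be randomized with a stratified block randomization scheme (with a random block size of 4, 6, and 8 participants". The same section fixes the size ("Patient enrollment will conclude when 34 subjects, 17 of each group, have been enrolled in the study") and justifies it by "80% power to detect a difference between groups of the minimum clinically meaningful effect size of 1.5 points or greater", with "an assumed standard deviation for VAS score of 1.5 points" and a two-sample test.

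Plan for Analysis of Results gives the primary test: "A two-sample t-test will be used to assess differences in the primary outcome of change in VAS score after procedure between groups". It then adds: "Multivariate linear/logistic regression models may be used to assess the impact of other variables onto primary or secondary outcomes". That sentence is permissive, does not mention the strata, and does not replace the t-test.

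The text available for this review names no stratification factor. The opening page and the design figure were not available, so the factor may be named there. Participant Recruitment Methods lists three locations, but nothing says that site is the stratifier.

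**The concern.** Stratified blocking makes the arms nearly balanced within each stratum, so the difference in means carries little of the variation between strata. An analysis with a stratum term recognises this. A pooled two-sample t-test does not: it counts between-stratum variation as random error and reports too large a standard error. The consequence is lost efficiency. False positives are not inflated, and the stated power is not undermined.

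Two limits apply from the start. If the strata do not predict change in VAS, nothing is lost. And because the outcome is a change score, a stratum difference that affects the scores before and after the procedure equally cancels out; only strata related to the change itself matter.

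**Working it through.** **Inputs from the protocol.** Difference 1.5; SD 1.5 (stated for VAS score, taken here as the total SD of change in VAS); two-sided α 0.05; 17 per arm; blocks of 4, 6 and 8 within strata.

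**Assumptions, because the documents give no figure.** Number of strata K = 2, 3, 4 or 6, equally likely; share of outcome variance explained by strata, R², from 0 to 30%.

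**1. Reproduce the plan's sample size.** For the two-sample t-test the noncentrality is 1.5 / (1.5 × √(2/17)) = 1/0.343 = 2.92, on 32 df. Exact two-sided power is 80.7% at 17 per arm and 78.1% at 16. So 17 per arm is the smallest number that reaches 80%, and the planned 34 is confirmed.

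**2. How far the t-test overstates its standard error.** The t-test works with roughly 1.5 × √(2/17) = 0.515 whatever the strata do. With perfect balance within strata, the true standard error is 0.515 × √(1 − R²):

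- R² = 10%: 0.515 × 0.949 = 0.488 (t-test too large by a factor 1.05)
- R² = 20%: 0.515 × 0.894 = 0.460 (factor 1.12)
- R² = 30%: 0.515 × 0.837 = 0.430 (factor 1.20)

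**3. Power of the adjusted model under perfect balance.** The noncentrality becomes 2.92/√(1 − R²), on 34 − K − 1 df. For K = 2, power is 80.6%, 82.6%, 84.5%, 88.4% and 92.1% at R² = 0, 5, 10, 20 and 30%. For K = 3 the figures are within 0.1 point of these.

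**4. Simulation with the actual block scheme.** Perfect balance is not assured, because the last block in each stratum is usually incomplete. Trials of 34 patients were therefore simulated with random blocks of 4, 6 and 8 within strata and equally spaced stratum effects. Each cell used 20,000 trials (simulation standard error about 0.15 point for type I error and 0.3 for power). Each entry gives 2 strata / 3 strata.

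| R² | t-test type I error, % | t-test power, % | Adjusted power, % | Gain, points |
|---|---|---|---|---|
| 0% | 4.9 / 4.8 | 80.5 / 80.5 | 80.2 / 80.1 | −0.3 / −0.4 |
| 5% | 4.6 / 4.6 | 81.1 / 80.8 | 82.4 / 81.9 | 1.3 / 1.1 |
| 10% | 4.1 / 4.2 | 81.4 / 81.2 | 84.1 / 83.8 | 2.7 / 2.6 |
| 20% | 3.0 / 3.0 | 82.6 / 82.6 | 88.0 / 87.7 | 5.4 / 5.1 |
| 30% | 2.2 / 2.2 | 84.0 / 83.6 | 91.9 / 91.7 | 7.9 / 8.1 |

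The adjusted model's type I error was 4.7% to 5.2% in every cell.

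**5. More strata.** With 4 non-prognostic strata, power is 80.7% unadjusted and 79.6% adjusted. With 6 strata (unadjusted/adjusted) it is 80.7/78.7% at R² = 0, 80.5/80.0% at 5%, 81.5/82.4% at 10%, 82.6/86.9% at 20% and 83.4/90.7% at 30%. Of the 2.0-point loss at R² = 0 with 6 strata, about 0.4 is degrees of freedom (a perfectly balanced model on 27 df has 80.25%, against 80.7%). The rest is imbalance within strata.

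**6. Independent repeat.** A separately written simulation (K = 2 to 4, also 20,000 trials per cell) gave t-test type I error of about 3.9%, 3.0–3.2% and 2.0–2.3% at R² = 10, 20 and 30%. Power (unadjusted vs adjusted) was 81–82% vs 83–85%, 82–83% vs 87–88%, and 84% vs 92%. This agrees with step 4 within simulation error.

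**The case against.** The strongest reply is that nothing the plan promises fails. It promises 80% power with a two-sample test and then uses that test; the unadjusted power is about 80% or better in every scenario and rises as the strata become more prognostic. That is correct, and for that reason this is a point about efficiency only.

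The benefit also depends on facts not in view. The factors, their number and their prognostic strength are unknown, and strata explaining 20–30% of the variance of a change score may be optimistic. At 5–10% the gain is only about 1 to 3 points. This stands, so the result is given as a range beginning at zero, and the absence of a named factor is not held against the plan.

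An unconditional switch can also cost power: with 4 or 6 non-prognostic strata the adjusted model falls to 79.6% or 78.7%, just under target. This stands as well, and is a reason to keep the strata few. The simulations assumed equally likely strata, which the documents neither support nor exclude. Nor does the visible analysis plan call for a confidence interval, so a wider interval matters only if one is reported.

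The claim that the optional regression already covers the point does not stand. It names no strata and is not the primary test, and an adjusted result selected after seeing the data could not carry the main conclusion.

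**Conclusion.** The concern holds in its conditional form. The allocation uses strata and the primary test does not. If the strata predict change in VAS, the t-test is conservative, and with 2 or 3 strata it forgoes about 1, 3, 5 or 8 points of power when they explain 5, 10, 20 or 30% of the variance. If they explain nothing, there is no harm in the planned test. These sizes rest on the assumed variance shares, equally likely strata and a total SD of 1.5 for the change score.

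This is a change that should be made, not a defect of validity. The planned sample is the smallest that reaches 80%, so efficiency that needs no further patients is worth having. Confidence is medium because the strata are not known.

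**What to change.** State the stratification factors and their levels, if this is not already done in material outside this review. Specify the primary analysis as a linear model of change in VAS on treatment arm plus the randomisation strata, two-sided at 0.05, in place of the unadjusted t-test. Keep the number of strata small for 34 patients.

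The cost is protocol and SAP wording only, with no added data or patients. The model spends one residual degree of freedom per stratum beyond the first. If the strata turn out not to be prognostic, the price is under 0.5 point of power with 2 or 3 strata, about 1 with 4 and about 2 with 6.

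A minor clarification can go in at the same time: give the target as 34 participants randomised 1:1, about 17 per arm, and do not close enrolment by arm. Random blocks within strata give exactly 17/17 at patient 34 in only about 51% of trials with 2 strata and 42% with 3. An uneven split costs little: t-test power is 80.7% at 17/17 and 80.2% at 15/19.

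### The sample size reproduces, but its SD is labelled for the VAS score while the primary test is on change in VAS; adjusting for pre-procedure VAS largely removes the dependence on the unstated correlation

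*Combined protocol and SAP*

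**What the plan says.** The Objectives section lists the primary outcome as "VAS pain scores measured on a 10 point scale before and after PNE procedure". The null hypothesis in the same section is of "no significant difference in change in VAS score between patients in the lidocaine patch group" and the control group. Plan for Analysis of Results names the test: "A two-sample t-test will be used to assess differences in the primary outcome of change in VAS score after procedure between groups". It sets a two-sided 0.05 level and allows regression models as an optional extra.

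The sample-size text in Study Design/Methodology has two statements of the target. One reads "The trial is powered to detect a change in VAS pain score of 1.5 points or more on a 10 point scale". The other claims "80% power to detect a difference between groups of the minimum clinically meaningful effect size of 1.5 points or greater", using a two-sample test at 0.05 with "an assumed standard deviation for VAS score of 1.5 points". Enrolment is 34 patients, 17 per group. The two citations there support the 1.5-point threshold; none is attached to the SD.

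On timing, the study design text says "VAS pain scores prior to and immediately after procedure will be recorded". The data list under Research Materials, Records, and Privacy has "VAS pain score prior to and after the PNE procedure". Neither says whether the first score is taken before the patch goes on or after it has been worn.

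**The concern.** The SD in a sample-size calculation must be the SD of the variable that will be tested. Here the variable tested is a difference between two scores in the same patient, and the SD carries the label of the score. The two SDs coincide only in particular circumstances; for example, when the pre and post SDs are equal they match only at a correlation of 0.5.

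The text supports two readings. Under the first, 1.5 is the SD of change: the same paragraph describes the target as a change and sizes the trial with the type of test later applied to change. Under the second, 1.5 is the SD of a single score: elsewhere the plan uses the plain term for the separate before and after measurements, and adds the word change when it means the difference. Nothing settles the matter.

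What is at stake is whether the stated 80% belongs to the planned test. There is little slack, since the largest SD of change that keeps 80% power with 17 per arm is 1.514.

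**Working it through.** **Inputs from the plan.** n = 17 per arm, difference 1.5, SD 1.5, two-sided alpha 0.05 and target power 80%. Every pre-procedure SD and every correlation below is an assumption, because the plan gives none.

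**Step 1: reproduce the stated size.** Two-sample t-test, noncentral t, df = 2 × 17 − 2 = 32, critical value 2.037. Noncentrality = 1.5 / (1.5 × √(2/17)) = √8.5 = 2.915. Power is 80.7%. With 16 per arm it is 78.1%, so 17 is the smallest size that reaches 80%. The plan's arithmetic is right.

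**Step 2: reading 1, where 1.5 is the SD of change.** The step 1 calculation is then the power of the planned test, 80.7%.

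**Step 3: reading 2, where 1.5 is the post-procedure SD.** With pre-procedure SD s0 and correlation r:

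SD of change = √(s0² + 1.5² − 2 × r × s0 × 1.5)

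For example, s0 = 1.5 and r = 0 give √(2.25 + 2.25) = 2.121. Each cell shows the SD of change and the power of the change-score t-test with 17 per arm.

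| Pre SD (assumed) | r = 0 | r = 0.3 | r = 0.5 | r = 0.7 | Smallest r for 80% |
|---|---|---|---|---|---|
| 1.5 | 2.121: 51.6% | 1.775: 66.6% | 1.500: 80.7% | 1.162: 95.4% | 0.49 |
| 1.0 | 1.803: 65.3% | 1.533: 79.0% | 1.323: 89.3% | 1.072: 97.7% | 0.32 |
| 0.5 | 1.581: 76.5% | 1.432: 84.2% | 1.323: 89.3% | 1.204: 94.1% | 0.14 |

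Power can therefore fall on either side of 80%.

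**Step 4: the same trial with a baseline-adjusted model.** Regress post-procedure VAS on group and pre-procedure VAS, with df = 31. Power is averaged over chance baseline imbalance (R² of group on baseline distributed as Beta(0.5, 16)).

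- If 1.5 is the post-procedure SD, the residual SD is 1.5 × √(1 − r²), whatever the pre-procedure SD. At r = 0, 0.3, 0.5 and 0.7 this is 1.500, 1.431, 1.299 and 1.071, and power is 79.4%, 83.0%, 89.4% and 97.3%.
- If 1.5 is the SD of change, the residual SD cannot exceed 1.5. Regression picks the slope b that minimises the variance of post − b × pre, and b = 1 gives the change itself. The worst case is again 79.4%. With equal pre and post SDs the residual SD is 1.5 × √((1 + r)/2), and power at the same correlations is 97.5%, 93.1%, 89.4% and 85.4%.

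**Step 5: what the model costs.** Its largest loss against the change-score t-test, over pre SD 0.25 to 2.0 and r = 0 to 0.9 with post SD 1.5, is 1.3 percentage points. If the SD of change and the residual SD are both 1.5, power goes from 80.7% to 79.4%.

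**The case against.** The strongest reply is that this may be only a label. The sample-size paragraph says the trial is powered for a change and uses the type of test that the analysis section applies to change. On that reading 1.5 is the SD of the analysed variable and only the label needs correcting. This stands as one of two open readings, but the label does not exclude the other.

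A reader might infer that the trial is underpowered, with 52% as its real power. The documents do not support that. The figure needs three conditions that appear nowhere: a single-score SD, equal SDs before and after, and zero correlation. Pain before the procedure may well vary less than pain after it, in a population with overactive bladder and chronic pain excluded as an indication; that too is an assumption. At a pre-procedure SD of 0.5 the lowest power in the table is 76.5%.

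A reader might also infer that a non-significant result could not be interpreted. That goes too far: the confidence interval will use the observed SD. The ambiguity affects planning.

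Finally, a t-test on change is valid in a randomised trial, and a baseline-adjusted model does not identify where 1.5 came from. Both statements are correct, so the SD must still be named and justified. What the model adds is a power figure that holds under either meaning of 1.5.

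**Conclusion.** The concern holds as a mismatch between the SD and the endpoint. The stated size is correct for its inputs (80.7%), and no loss of power is shown. If 1.5 is the SD of change, the stated power applies to the planned test. If 1.5 is the post-procedure SD, the planned test's power is undetermined, with the range in step 3 resting wholly on assumed pre-procedure SDs and correlations.

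The case for a change of analysis is that the planned unadjusted test is sensitive to a correlation the plan does not state, while a model using a score already collected has a floor of about 79% under either meaning of 1.5. That floor assumes the 1.5 is right for whichever quantity it describes, a linear relation with a common slope, and all 34 patients analysed. It is marginally under the 80% target in the worst case.

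**What to change.** In Plan for Analysis of Results, replace the primary-test sentence with: *Post-procedure VAS will be compared between groups in a linear model adjusted for pre-procedure VAS, recorded before the patch is applied, at a two-sided significance level of 0.05.*

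In the study design text, fix the first VAS before the patch is applied. A score taken after the patch has been worn could already carry a treatment effect, which would spoil it as a covariate and also distort a change score.

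In the sample-size text, say which SD 1.5 is and give its basis, then state power for the model: *With 17 per group, and an SD of 1.5 for [post-procedure VAS / change in VAS], power for a 1.5-point difference is about 79% or more at any pre/post correlation.* If the SD is post-procedure, add 79%, 83%, 89% and 97% at correlations of 0, 0.3, 0.5 and 0.7. Align the change-based wording in the Objectives and the sample-size text with the model.

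The cost is one degree of freedom, at most about 1.3 points of power against the change-score t-test, a fixed time for a score already collected, and matching edits in those four places. No extra patients are needed.

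### Does the after-procedure VAS measure pain during the PNE, or only the pain left when it is over?

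*Combined protocol and SAP*

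**What the plan says.** The Objectives section gives the primary outcome as "VAS pain scores measured on a 10 point scale before and after PNE procedure" and predicts that patch patients "will experience significantly less pain at the time of PNE as measured by change in VAS pain score". In the Study design section every woman receives injected 1% lidocaine and then has the PNE. The section adds: "If inadequate analgesia is reported by the Patient during the procedure, additional injectable lidocaine will be administered". On timing it says "VAS pain scores prior to and immediately after procedure will be recorded". The Plan for Analysis of Results compares the change in VAS between groups with a two-sided two-sample t-test at 0.05.

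The Research Materials section lists the VAS as taken before and after the procedure and says the VAS and satisfaction templates are appendices; they are not in the reviewed text. Volume of injected lidocaine and satisfaction are named secondary outcomes. The sample size of 17 per group rests on a 1.5-point difference and "an assumed standard deviation for VAS score of 1.5 points".

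**The concern.** A score taken immediately after the PNE can answer two questions: how much it hurt, or how much it hurts now. The hypothesis concerns the first, and the visible outcome definition does not say which is asked.

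The difference could matter because extra lidocaine is triggered by pain. If the patch works, more controls than patch patients would be topped up, and a current-pain score taken afterwards would bring the arms closer together. Brief procedural pain may also have eased by then. Part of a real benefit could then appear as a smaller lidocaine volume, while the primary difference fell below the 1.5 points the trial is sized to detect.

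A smaller point concerns the baseline. The patch is worn for 30 minutes and is described as "producing analgesia within 30 minutes", yet the score before the procedure is not timed against it. A baseline taken with the patch already acting would subtract part of the effect from the change score.

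**Working it through.** **1. The plan's own figure.** Inputs from Study Design/Methodology: difference 1.5, SD 1.5, 17 per arm, two-sided α = 0.05. The noncentrality is 1.5 / (1.5 × √(2/17)) = 2.92 on 32 degrees of freedom, with critical t 2.037. Power is 80.7%; with 16 per arm it is 78.1%. So 17 is the smallest number per arm that reaches 80%, and the stated size reproduces.

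**2. Top-ups, if current pain is scored.** The documents give no inputs for this, so all are assumed. Control pain is normal with mean μ and SD 1.5, clipped to 0–10. The patch shifts the mean by −1.5. A woman whose pain reaches a threshold T is topped up, which lowers her score by 1, 2 or 3 points (floor 0). Power is for the after-procedure score with 17 per arm.

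| T | μ | Topped up, control / patch | 1 point | 2 points | 3 points |
|---|---|---|---|---|---|
| 6 | 4 | 9% / 1% | 81% | 80% | 76% |
| 6 | 5 | 25% / 5% | 80% | 72% | 56% |
| 6 | 6 | 50% / 16% | 77% | 60% | 25% |
| 4 | 5 | 75% / 37% | 76% | 56% | 18% |

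The measured difference shrinks as well. Across all scenarios run, a 1-point top-up leaves 1.1 to 1.4 of the 1.5 points. At μ = 2 the zero floor alone already reduces it to 1.18.

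Run as a change score with a low baseline (SD 0.56), the same model gives 71–81% for a 1-point effect. It gives 50% when half the controls have a 2-point top-up, and 11% at its worst (76% of controls topped up, 3 points).

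**3. Settling, with no top-ups.** Suppose pain fades to a fraction f before scoring, and e points of the 1.5 SD are scoring noise that does not fade. Then the difference is 1.5f and the SD is √(f²(1.5² − e²) + e²). For f = 0.5 the difference is 0.75:
- e = 0: SD 0.75, power 80.7%. Signal and spread shrink together, so power is unchanged.
- e = 0.5: SD 0.866, power 69%.
- e = 0.75: SD 0.992, power 57%.

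**4. Baseline timing.** If the patch lowered the baseline by 0.1, 0.25 or 0.5 points, the difference would be 1.4, 1.25 or 1.0, and power 75%, 65% or 47% with SD 1.5. The largest loss needs the patch to remove half a point of resting pain. Resting pain is probably low (an assumption), since the exclusion criteria list "Chronic pain as an indication for the PNE procedure".

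**5. The alternative primary outcome.** If recalled worst pain had SD 2.0, 17 per arm would give 56% power for 1.5 points and 29 per arm would be needed for 80%. With SD 2.5 the figures are 40% and 45 per arm. These SDs are also assumed.

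**The case for a change.** The strongest argument for acting is that this is the primary outcome, the gap is real in every visible section, and a recall question not asked at the visit cannot be properly recovered later. One line on a form costs almost nothing. Power also understates the matter, because the estimate itself shrinks: a patch that met the 1.5-point threshold during the procedure could be reported as falling short.

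Part of this stands. The visible text is silent on the recall period, and a current-pain score could understate a difference in procedural pain. It is also true that the hypothesis shows intent without defining the item put to the patient.

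What does not follow is a fault in the plan. The concern applies only if the unseen template asks about current pain. Even then, pain after extra analgesia as needed, read beside the volume used, is a legitimate comparison of the two strategies. Adding worst pain as a secondary outcome would leave the primary and any loss in it untouched. Making it primary carries its own possible loss, and prompt top-ups could still limit worst pain.

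**Conclusion.** No change is called for. The missing recall period is a detail of the VAS item, and the protocol assigns that item to an appended template. The hypothesis points to procedural pain, and scoring immediately afterwards limits settling. If the template asks about pain during the PNE, the concern largely falls away. If it asks about current pain, the randomised comparison remains valid, and lidocaine volume and satisfaction can show benefit that the primary score misses.

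No figure in the plan is shown to be wrong. The loss is negligible if top-ups are rare or weak, and material only if they are common and strong or if pain fades a lot before scoring against fixed noise. The documents do not say which holds, and a range from 11% to 81% on assumed inputs is not evidence of harm. The choice between current pain and recalled worst pain is a fair trade-off. Taking the baseline after consent and before the patch is a sensible way to fill an unstated detail: the Informed Consent Process already puts consent before the patch, and the gain is probably small.
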